2. ARM DROPPING

The patient and the examiner both raise their arms to shoulder height and let them fall to their sides. In a normal subject, a stout slap is heard as the arms hit the sides. In the patient with extreme Parkinson's syndrome, the arms fall very slowly:

- 0 Normal, free fall with loud slap and rebound
- 1 Fall slowed slightly with less audible contact and little rebound
- 2 Fall slowed, no rebound
- 3 Marked slowing, no slap at all
- 4 Arms fall as though against resistance; as though through glue

3. SHOULDER SHAKING

The patient's arms are bent at a right angle at the elbow and are taken one at a time by the examiner who grasps one hand and also clasps the other around the patient's elbow. The patient's upper arm is pushed to and fro and the humerus is externally rotated. The degree of resistance from normal to extreme rigidity is scored as follows:

- 0 Normal
- 1 Slight stiffness and resistance
- 2 Moderate stiffness and resistance
- 3 Marked rigidity with difficulty in passive movement
- 4 Extreme stiffness and rigidity with almost a frozen shoulder

4. ELBOW RIGIDITY

The elbow joints are separately bent at right angles and passively extended and flexed, with the patient's biceps observed and simultaneously palpated. The resistance to this procedure is rated. (The presence of cogwheel rigidity is noted separately.)

- 0 Normal
- 1 Slight stiffness and resistance
- 2 Moderate stiffness and resistance
- 3 Marked rigidity with difficulty in passive movement
- 4 Extreme stiffness and rigidity with almost a frozen joint

5. FIXATION OF POSITION OR WRIST RIGIDITY

The wrist is held in one hand and the fingers held by the examiner's other hand, with the wrist moved to extension, flexion and ulner and radial deviation:

- 0 Normal
- 1 Slight stiffness and resistance
- 2 Moderate stiffness and resistance
- 3 Marked rigidity with difficulty in passive movement
- 4 Extreme stiffness and rigidity with almost a frozen joint

6. LEG PENDULOUSNESS

The patient sits on a table with his legs hanging down and swinging free. The ankle is grasped by the examiner and raised until the knee is partially extended. It is then allowed to fall. The resistance to falling and the lack of swinging form the basis for the score on this item:

- 0 The legs swing freely
- 1 Slight diminution in the swing of the legs
- 2 Moderate resistance to swing
- 3 Marked resistance to damping of swing
- 4 Complete absence of swing

7. HEAD DROPPING

The patient lies on a well-padded examining table and his head is raised by the examiner's hand. The hand is then withdrawn and the head allowed to drop. In the normal patient the head will fall upon the table. The movement is delayed in extrapyramidal system disorder and in extreme parkinsonism it is absent. The neck muscles are rigid and the head does not reach the examining table. Scoring is as follows:

- 0 The head falls completely with a good thump as it hits the table
- 1 Slight slowing in fall, mainly noted by lack of slap as head meets the table
- 2 Moderate slowing in the fall quite noticeable to the eye
- 3 Head falls stiffly and slowly
- 4 Head does not reach examining table

8. GLABELLA TAP

Patient is told to open eyes wide and not to blink. The glabella region is tapped at a steady, rapid speed. The number of times patient blinks in succession is noted:

- 0 0-5 blinks
- 16-10 blinks
- 2 11-15 blinks
- 3 16-20 blinks
- 421 and more blinks

9. TREMOR

Patient is observed walking into examining room and is then reexamined for this item:

- 0 Normal
- 1 Mild finger tremor, obvious to sight and touch
- 2 Tremor of hand or arm occurring spasmodically
- 3 Persistent tremor of one or more limbs
- 4 Whole body tremor

10. SALIVATION

Patient is observed while talking and then asked to open his mouth and elevate his tongue. The following ratings are given:

- 0 Normal
- 1 Excess salivation to the extent that pooling takes place if the mouth is open and the tongue raised
- 2 When excess salivation is present and might occasionally result in difficulty in speaking
- 3 Speaking with difficulty because of excess salivation
- 4 Frank drooling

12.9 Personal and Social Performance Scale

The rating is based on four main areas: (a) socially useful activities, including work and study; (b) personal and social relationships; (c) self-care; and (d) disturbing and aggressive behaviors. Data will be captured in the following format using the PSP descriptions provided below:

	Absent	Mild	Manifest	Marked	Severe	Very Severe
a. Socially useful activities, including work and study						
b. Personal and social relationships						
c. Self-care						
d. Disturbing and aggressive behaviors						
For areas a-c, the degrees of sev	erity are:					
Absent						
Mild	Not manifest difficulties, known only to someone who is very familiar with the person					
Manifest, but not marked	Difficulties clearly noticeable by everyone, but not interfering substantially with the person's ability to perform his/her role in that area, given the person's socio-cultural context, age, sex and educational levels					
Marked	Difficulties heavily interfering with role performance in that area; however, the person is still able to do something without professional or social help, although inadequately and/or occasionally; if helped by someone, he/she may be able to reach the previous level of functioning					
Severe	Difficulties that make the person unable to any role performance in that area, if not professionally helped, or lead the person to a destructive role; however, there are no survival risks.					
Very severe	Impairments and difficulties of such intensity to endanger person's survival.					
For area d, the degrees of severi	ity are:					
Absent						
Mild	Mild rudeness, unsociability or whingeing					
Manifest, but not marked	Speaking too loudly or speaking to others in a too-familiar manner, or eating in a socially unacceptable manner					
Marked	Insulting other in public, breaking or wrecking objects, acting frequently in a socially inappropriate but not dangerous way (eg, stripping in public or urinating in public).					
Severe	Frequent verbal threats or frequent physical assaults, without intention or possibility of severe injuries.					
Very severe	Frequent aggressive acts, aimed at or likely to cause severe injuries.					

Occasional is defined as occurring three or more times in the reference period or occurring even less than three times but in circumstances and/or with such a previous history to convince the rater that there is a risk of recurrence in the near future. If the aggressive behavior has been present occasionally, the rating may be decreased by one degree, eg, from severe to marked.

[figure not shown]
*Main areas: a=socially useful activities, including work and study; b=personal and social relationships; c=self-care; d=disturbing and aggressive behaviors.

[figure not shown]
Guidelines for PSP Total Score

[figure not shown]
- Ratings from 71-100 reflect only mild difficulties.
- Ratings from 31-70 reflect manifest disabilities of various degrees.
- Ratings from 1-30 reflect functioning so poor that intensive support or supervision is needed.

The levels of functioning in other areas should be taken into account to adjust the rating inside the decimal level (for instance, from 31 to 40). Suicidal risk is not included in the scale.

10-point Intervals	PSP Descriptions
100 – 91	Excellent function in all four main areas*. He/she is held in high consideration for his/her qualities, copes adequately with life problems, is involved in a wide range of interests and activities
90 – 81	Good functioning in all four main areas, presence of only common problems or difficulties
80 - 71	Mild difficulties in 1 or more areas of a-c
70 – 61	Manifest, but not marked difficulties in 1 or more areas of a-c or mild difficulties in d
60 - 51	Marked difficulties in 1 of areas a-c, or manifest difficulties in d
50 – 41	Marked difficulties in 2 or more, or severe difficulties in 1 of areas a-c, with or without manifest difficulties in d
40 - 31	Severe difficulties in 1 and marked difficulties in at least 1 of areas a-c, or marked difficulties in d
30 - 21	Severe difficulties in 2 of areas a-c, or severe difficulties in d, with or without impairment in areas a-c
20 - 11	Severe difficulties in all areas a-d or very severe in d with or without impairment in general areas a-c. If the person reacts to external prompts the suggested score are 20-16, if not, the suggested scores are 15-11
10 - 1	Lack of autonomy in basic functioning with extreme behaviours but without survival risk (ratings 6-10) or with survival risk, eg, death risk due to malnutrition, dehydration, infections, inability to recognize situations of manifest dander (ratings 5-1)

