10.3 ADDITIONAL EFFICACY PARAMETERS

The overall relapse rate, as well as the relapse rates for sub-categories of interest including modified manic episode and modified depressive episode will be presented.

Time to early discontinuation with any reason (including relapse) during the DBTP for the DB ITT population will be analyzed using the same method used to analyze the primary efficacy variable.

For the following continuous efficacy variables, the change from baseline refers to the change from OL baseline during the OLTP, and the change from DB baseline during the DBTP, unless stated otherwise.

For Open-label Treatment Period

- Change from baseline in YMRS total score by visit
- Change from baseline in MADRS total scores by visit
- Change from baseline in CGI-S score by visit
- CGI-I score by visit
- Change from baseline in PSP total score and sub-domain score by visit

For Double-blind Treatment Period

- Change from DB baseline in YMRS total score by visit
- Change from DB baseline in MADRS total score by visit
- Change from DB baseline in CGI-S score by visit
- CGI-I score by visit
- Change from DB baseline in PSP total score and sub-domain score by visit

Descriptive statistics (n, mean, standard deviation, median, Q1, Q3, minimum and maximum) for additional efficacy parameters will be provided by visit for the OL ITT population and the DB ITT population using both last-observation-carried forward (LOCF) and observed cased (OC) approaches. LOCF approach will be used to impute missing postbaseline values. Imputation of missing values will be done for the OLTP and the DBTP separately.

For the DBTP, the additional efficacy parameters will be analyzed by using a mixed-effects model for repeated measures (MMRM) with treatment group, region (US and non-US), modified index episode strata (manic or depressive), visit, and treatment group-by-visit interaction as fixed effects and the baseline value and baseline-by-visit interaction as the covariates. An unstructured covariance matrix will be used. The Kenward-Roger approximation ([Kenward and Roger, 1997](#)) will be used to estimate denominator degrees of freedom. The analysis will be performed based on post-DB baseline scores using only the OC without imputation of missing values. Least squares mean and their standard errors based on the MMRM analysis will be plotted by treatment group and visit.

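### The PSP area d note defines occasional aggression as three or more times and then allows a milder rating for it, which contradicts the scale's own anchors built on frequent behaviour (minor)

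*Protocol*

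**What the plan says.** Protocol Attachment 12.9 reproduces the PSP and says that data are captured with the descriptions it prints, so the text is an operative scoring instruction. Protocol 6.2.2.2 refers to the same attachment.

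Three elements bear on area d:

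- **The definition.** "Occasional is defined as occurring three or more times in the reference period or occurring even less than three times". The second limb applies when circumstances or previous history are enough "to convince the rater that there is a risk of recurrence in the near future".
- **The consequence.** "If the aggressive behavior has been present occasionally, the rating may be decreased by one degree, eg, from severe to marked".
- **The anchors.** Severe is "Frequent verbal threats or frequent physical assaults, without intention or possibility of severe injuries". Very severe is "Frequent aggressive acts, aimed at or likely to cause severe injuries". Marked has three clauses, one of which depends on acting frequently in an inappropriate but not dangerous way. The text shown does not define frequent.

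On use, Protocol 7.2.3 and 7.3.3 list PSP change as an other efficacy variable, with descriptive statistics only. SAP 10.3 lists "Change from DB baseline in PSP total score and sub-domain score by visit" and applies an MMRM to the additional efficacy parameters in the double-blind period. It names disturbing and aggressive behaviours as one of the sub-domains, so area d is analysed in its own right as well as through the total.

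**The concern.** A rule that softens a rating for occasional behaviour should apply to infrequent acts. Here the word is defined by a minimum count with no ceiling, and the only cases left outside it are the least frequent ones. The same patient can therefore satisfy both an anchor that demands frequent acts and the exception to it.

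What is at stake is the consistency of one sub-domain and, through it, some PSP totals. A rater who follows the note literally and one who notices the contradiction can score the same patient a full degree apart. The PSP is rated at Visits 2, 6, 12, 16, 22 and 31/ET. Visit 2, in the acute episode, and Visit 31/ET, which relapsing patients reach because relapse requires discontinuation, are the visits where area d is most likely to matter.

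**Working it through.** The plan gives no figure to reproduce. The check is a logical reading of the note, followed by simple arithmetic on the total-score bands.

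**Step 1. Apply the note as printed.**

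| Behaviour in the reference period | Occasional by the definition? | One-degree reduction? |
|---|---|---|
| Three or more times, no upper limit | Yes | Permitted |
| Fewer than three, risk of recurrence | Yes | Permitted |
| Fewer than three, no risk of recurrence | No | Not permitted |

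The reduction is available in the two more worrying rows and withheld in the least worrying one.

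**Step 2. Compare with the anchors.** Any patient with three or more acts who meets the severe or very severe anchor also meets the printed definition of occasional. Because that definition has no upper limit, no number of acts separates the anchor from its exception.

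**Step 3. See which way the definition leans.** The second limb brings in patients with few acts because they may recur. That is how one widens a category of greater concern, not one that earns a milder score. The threshold therefore appears to describe behaviour that is frequent, ie, not occasional. This is an inference from the structure of the text; the source version of the scale was not available to confirm it.

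**Step 4. Size.** Bands for area d in the Attachment 12.9 table:

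- very severe in d: 20–11
- severe in d: 30–21 ("severe difficulties in d, with or without impairment in areas a-c")
- marked in d: 40–31 ("Severe difficulties in 1 and marked difficulties in at least 1 of areas a-c, or marked difficulties in d")
- manifest in d: 60–51

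Differences between lower bounds for a one-degree reduction:

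- very severe to severe: 21 − 11 = 10 points
- severe to marked: 31 − 21 = 10 points
- marked to manifest: 51 − 31 = 20 points, because no area d degree by itself selects the 50–41 band

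These shifts hold only where area d alone sets the band. Two examples show how areas a–c can absorb them. With marked d and marked difficulties in two of a–c, reducing d moves the band from 40–31 to 50–41, which is 41 − 31 = 10 points instead of 20. With marked d, severe difficulties in one of a–c and marked in another, the band stays at 40–31 and the shift is 0.

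The manifest-to-mild step is left out. Those degrees concern loud or over-familiar speech, poor manners and rudeness, whereas the note is about aggressive behaviour.

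**The case against.** The strongest reply is that this is an awkward sentence that experienced raters will not apply backwards. Protocol 6.2.2.2 requires trained raters with extensive experience, and Attachment 12.13.2 requires study-certified raters for remote and in-home efficacy assessments. The reduction is permissive, and a patient with frequent assaults meets the severe anchor directly. Exclusion criterion 8 removes patients at imminent risk of injuring others or causing significant property damage, which should thin out the highest area d ratings. Randomized patients must be in remission, so little aggression is expected at double-blind baseline. A word may also have been lost when the page was read, although the sentence is complete and starts with a capital.

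Much of this stands and limits the weight of the point. It does not remove the contradiction: no other section corrects the note, and nothing shown tells raters to disregard it.

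A reader might go on to infer more than the documents support:

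- *That frequent aggression is systematically downgraded.* The text permits a reduction and does not require one. Nothing shows that any rater used it this way, and the rater worksheet is not in the documents.
- *That open-label improvement and loss of function at relapse are understated.* This would need the note to be applied literally at Visit 2 and at Visit 31/ET, in an unknown number of patients.
- *That the problem is concentrated in manic-index patients.* Disruptive/aggressive behaviour is one of four YMRS items, of which two must reach the threshold, so a patient can qualify without it.
- *That the treatment comparison is biased.* The same note applies in every arm under blinding, and no differential use is shown.

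**Conclusion.** The note in Attachment 12.9 is wrong as written. Its definition of occasional and its one-degree reduction cannot both stand beside anchors that require frequent acts. The possible effect on an individual PSP total is 10 or 20 points where area d alone sets the band, and smaller, down to zero, where areas a–c also hold it down. The number of patients affected cannot be derived from the documents.

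The consequence for the trial is minor. The PSP is outside the relapse definition (Protocol 4.7) and outside the sequential tests (Protocol 7.3.1, SAP 10.1), and it is not a secondary variable. The primary endpoint, power and Type I error do not depend on it. What remains is avoidable rater variation in the PSP total and the area d sub-domain. The conclusion rests on the printed wording being what raters were given.

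**What to change.** 1. Check the note against the source version of the scale and against the rater worksheet.
2. Correct it so that the one-degree reduction applies only to behaviour below the threshold of three or more times or a risk of recurrence. That threshold appears to define frequent behaviour; the final wording should follow the source scale.
3. Send raters a short memo.
4. Before unblinding, review area d ratings of marked or worse where source notes allow. Otherwise, state the limitation when reporting the PSP total and area d results.

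The cost is a one-line correction, a memo and a limited review. The review may be incomplete, because the capture format in Attachment 12.9 shows one degree per area and no flag for a rating that was reduced. The analysis models need no change.

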12.11 Columbia-Suicide Severity Rating Scale

COLUMBIA-SUICIDE SEVERITY RATING SCALE

(C-SSRS)

Baseline Version 1/14/09

Posner, K.; Brent, D.; Lucas, C.; Gould, M.; Stanley, B.; Brown, G.; Fisher, P.; Zelazny, J.; Burke, A.; Oquendo, M.; Mann, J.

Disclaimer:

This scale is intended for use by trained clinicians. The questions contained in the Columbia-Suicide Severity Rating Scale are suggested probes. Ultimately, the determination of the presence of suicidality depends on clinical judgment.

Definitions of behavioral suicidal events in this scale are based on those used in The Columbia-Suicide History Form, developed by [name] and [name], Conte Center for the Neuroscience of Mental Disorders (CCNMD), New York State Psychiatric Institute, [name]. (Oquendo M. A., Halberstam B. & Mann J. J., Risk factors for suicidal behavior: utility and limitations of research instruments. In M.B. First [Ed.] Standardized Evaluation in Clinical Practice, pp. 103-130, 2003.)

For reprints of the C-SSRS contact [name]., New York State Psychiatric Institute, [name]; inquiries and training requirements contact [contact]

SUICIDAL IDEATION	
Ask questions 1 and 2. If both are negative, proceed to "Suicidal Behavior" section. If the answer to question 2 is "yes," ask questions 3, 4 and 5. If the answer to question 1 and/or 2 is "yes", complete "Intensity of Ideation" section below.	Lifetime: Time He/She Felt Most Suicidal
1. Wish to be Dead Subject endorses thoughts about a wish to be dead or not alive anymore, or wish to fall asleep and not wake up. Have you wished you were dead or wished you could go to sleep and not wake up? If yes, describe:	Yes No
2. Non-Specific Active Suicidal Thoughts General, non-specific thoughts of wanting to end one's life/commit suicide (eg, "I've thought about killing myself") without thoughts of ways to kill oneself/associated methods, intent, or plan.	Yes No
Have you actually had any thoughts of killing yourself? If yes, describe: 3. Active Suicidal Ideation with Any Methods (Not Plan) without Intent to Act	Yes No
Subject endorses thoughts of suicide and has thought of at least one method during the assessment period. This is different than a specific plan with time, place or method details worked out (eg, thought of method to kill self but not a specific plan). Includes person who would say, "I thought about taking an overdose but I never made a specific plan as to when, where or how I would actually do itand I would never go through with it". Have you been thinking about how you might do this? If yes, describe:	
4. Active Suicidal Ideation with Some Intent to Act, without Specific Plan Active suicidal thoughts of killing oneself and subject reports having some intent to act on such thoughts, as opposed to "I have the thoughts but I definitely will not do anything about them". Have you had these thoughts and had some intention of acting on them? If yes, describe:	Yes No □ □
5. Active Suicidal Ideation with Specific Plan and Intent Thoughts of killing oneself with details of plan fully or partially worked out and subject has some intent to carry it out. Have you started to work out or worked out the details of how to kill yourself? Do you intend to carry out this plan? If yes, describe:	Yes No
INTENSITY OF IDEATION	
The following features should be rated with respect to the most severe type of ideation (ie,1-5 from above, with 1 being the least severe and 5 being the most severe). Ask about time he/she was feeling the most suicidal.	Most Severe
Most Severe Ideation: Type # (1-5) Description of Ideation	
Frequency How many times have you had these thoughts? (1) Less than once a week (2) Once a week (3) 2-5 times in week (4) Daily or almost daily (5) Many times each day	
Duration When you have the thoughts, how long do they last? (1) Fleeting - few seconds or minutes (4) 4-8 hours/most of day (2) Less than 1 hour/some of the time (5) More than 8 hours/persistent or continuous (3) 1-4 hours/a lot of time	
Controllability Could /can you stop thinking about killing yourself or wanting to die if you want to? (1) Easily able to control thoughts (4) Can control thoughts with a lot of difficulty (2) Can control thoughts with little difficulty (5) Unable to control thoughts (3) Can control thoughts with some difficulty (0) Does not attempt to control thoughts	
Deterrents Are there things - anyone or anything (eg, family, religion, pain of death) - that stopped you from wanting to die or acting on thoughts of committing suicide? (1) Deterrents definitely stopped you from attempting suicide (4) Deterrents most likely did not stop you (2) Deterrents probably stopped you (5) Deterrents definitely did not stop you (3) Uncertain that deterrents stopped you (0) Does not apply	
Reasons for Ideation What sort of reasons did you have for thinking about wanting to die or killing yourself? Was it to end the pain or stop the way you were feeling (in other words you couldn't go on living with this pain or how you were feeling) or was it to get attention, revenge or a reaction from others? Or both? (1) Completely to get attention, revenge or a reaction from others. (4) Mostly to end or stop the pain (you (2) Mostly to get attention, revenge or a reaction from others. (5) Completely to end or stop the pain and to end/stop the pain. (you couldn't go on living with the (0) Does not apply pain or how you were feeling).	

SUICIDAL BEHAVIOR	Lifetime						
(Check all that apply, so long as these are separate events; must ask about all types)							
Actual Attempt:	Yes No						
A potentially self-injurious act committed with at least some wish to die, as a result of act. Behavior was in part thought of as	пп						
method to kill oneself. Intent does not have to be 100%. If there is any intent/desire to die associated with the act, then it can	Total # of						
be considered an actual suicide attempt. There does not have to be any injury or harm, just the potential for injury or harm.							
If person pulls trigger while gun is in mouth but gun is broken so no injury results, this is considered an attempt.							
Inferring Intent: Even if an individual denies intent/wish to die, it may be inferred clinically from the behavior or circumstances. For example, a highly lethal act that is clearly not an accident so no other intent but suicide can be inferred	Yes No						
(eg, gunshot to head, jumping from window of a high floor/story). Also, if someone denies intent to die, but they thought that							
what they did could be lethal, intent may be inferred.							
Have you made a suicide attempt?							
Have you done anything to harm yourself?							
Have you done anything dangerous where you could have died?							
What did you do?							
Did you as a way to end your life?							
Did you want to die (even a little) when you? Were you trying to end your life when you ?							
Were you trying to end your life when you ?							
Or did you think it was possible you could have died from ?							
Or did you do it purely for other reasons / without ANY intention of killing yourself (like to relieve stress, feel							
better, get sympathy, or get something else to happen)? (Self-Injurious Behavior without suicidal intent)							
If yes, describe:							
Has subject engaged in Non-Suicidal Self-Injurious Behavior?							
Interrupted Attempt:	Yes No						
When the person is interrupted (by an outside circumstance) from starting the potentially self-injurious act (if not for that,							
actual attempt would have occurred).	Total # of						
Overdose: Person has pills in hand but is stopped from ingesting. Once they ingest any pills, this becomes an attempt rather	interrupted						
than an interrupted attempt. Shooting: Person has gun pointed toward self, gun is taken away by someone else, or is somehow prevented from pulling trigger. Once they pull the trigger, even if the gun fails to fire, it is an attempt. Jumping: Person is	interrupted						
poised to jump, is grabbed and taken down from ledge. Hanging: Person has noose around neck but has not yet started to hang							
- is stopped from doing so.							
Has there been a time when you started to do something to end your life but someone or something stopped							
you before you actually did anything?							
If yes, describe:							
Aborted Attempt:	Yes No						
When person begins to take steps toward making a suicide attempt, but stops themselves before they actually have engaged in	пп						
any self-destructive behavior. Examples are similar to interrupted attempts, except that the individual stops him/herself,	Total # of						
instead of being stopped by something else.							
Has there been a time when you started to do something to try to end your life but you stopped yourself							
before you actually did anything?							
If yes, describe:							

Preparatory Acts or Behavior:									
Acts or preparation towards imminently making a suicide attempt. This can include anything beyond a verbalization or									
thought, such as assembling a specific method (eg, buying pills, purchasing a gun) or preparing for one's death by suicide (eg,									
giving things away, writing a suicide note).									
Have you taken any steps towards making a suicide attempt or preparing to kill yours	elf (such as d	collecting							
pills, getting a gun, giving valuables away or writing a suicide note)?									
If yes, describe:									
Suicidal Behavior:			Yes No						
Suicidal behavior was present during the assessment period?									
Answer for Actual Attempts Only	Most Recent	Most Lethal	Initial/First						
	Attempt	Attempt	Attempt						
	Date:	Date:	Date:						
Actual Lethality/Medical Damage:	Enter Code	Enter Code	Enter Code						
0. No physical damage or very minor physical damage (eg, surface scratches).									
1. Minor physical damage (eg, lethargic speech; first-degree burns; mild bleeding; sprains).									
Moderate physical damage; medical attention needed (eg, conscious but sleepy, somewhat responsive; second-degree burns; bleeding of major vessel).									
3. Moderately severe physical damage; medical hospitalization and likely intensive care required									
(eg, comatose with reflexes intact; third-degree burns less than 20% of body; extensive									
blood loss but can recover; major fractures).									
4. Severe physical damage; medical hospitalization with intensive care required (eg, comatose									
without reflexes; third-degree burns over 20% of body; extensive blood loss with unstable									
vital signs; major damage to a vital area).									
5. Death									
Potential Lethality: Only Answer if Actual Lethality=0	Enter Code	Enter Code	Enter Code						
Likely lethality of actual attempt if no medical damage (the following examples, while having no									
actual medical damage, had potential for very serious lethality: put gun in mouth and pulled the									
trigger but gun fails to fire so no medical damage; laying on train tracks with oncoming train but									
pulled away before run over).									
0 = Behavior not likely to result in injury									
1 = Behavior likely to result in injury but not likely to cause death									
2 = Behavior likely to result in death despite available medical care									

COLUMBIA-SUICIDE SEVERITY RATING SCALE

Since Last Visit Version 1/14/09

Posner, K.; Brent, D.; Lucas, C.; Gould, M.; Stanley, B.; Brown, G.; Fisher, P.; Zelazny, J.; Burke, A.; Oquendo, M.; Mann, J.

Disclaimer:

This scale is intended for use by trained clinicians. The questions contained in the Columbia-Suicide Severity Rating Scale are suggested probes. Ultimately, the determination of the presence of suicidality depends on clinical judgment.

Definitions of behavioral suicidal events in this scale are based on those used in The Columbia-Suicide History Form, developed by [name] and [name], Conte Center for the Neuroscience of Mental Disorders (CCNMD), New York State Psychiatric Institute, [name]. (Oquendo M. A., Halberstam B. & Mann J. J., Risk factors for suicidal behavior: utility and limitations of research instruments. In M.B. First [Ed.] Standardized Evaluation in Clinical Practice, pp. 103-130, 2003.)

For reprints of the C-SSRS contact [name]., New York State Psychiatric Institute, [name]; inquiries and training requirements contact [contact]

SUICIDAL IDEATION							
Ask questions 1 and 2. If both are negative, proceed to "Suicidal Behavior" section. If the answer to question 2 is "yes", ask questions 3, 4 and 5. If the answer to question 1 and/or 2 is "yes", complete "Intensity of Ideation"	Since Last Visit						
section below.	Yes No						
1. Wish to be Dead Subject endorses thoughts about a wish to be dead or not alive anymore, or wish to fall asleep and not wake up.	1 65 140						
Have you wished you were dead or wished you could go to sleep and not wake up? If yes, describe:							
2. Non-Specific Active Suicidal Thoughts	Yes No						
General, non-specific thoughts of wanting to end one's life/commit suicide (eg, "I've thought about killing myself") without thoughts of ways to kill oneself/associated methods, intent, or plan during the assessment period. Have you actually had any thoughts of killing yourself? If yes, describe:							
3. Active Suicidal Ideation with Any Methods (Not Plan) without Intent to Act	Yes No						
Subject endorses thoughts of suicide and has thought of at least one method during the assessment period. This is different than a specific plan with time, place or method details worked out (eg, thought of method to kill self but not a specific plan). Includes person who would say, "I thought about taking an overdose but I never made a specific plan as to when, where or how I would actually do itand I would never go through with it." Have you been thinking about how you might do this? If yes, describe:							
4. Active Suicidal Ideation with Some Intent to Act, without Specific Plan	Yes No						
Active suicidal thoughts of killing oneself and subject reports having some intent to act on such thoughts, as opposed to "I have the thoughts but I definitely will not do anything about them." Have you had these thoughts and had some intention of acting on them? If yes, describe:							
5. Active Suicidal Ideation with Specific Plan and Intent	Yes No						
Thoughts of killing oneself with details of plan fully or partially worked out and subject has some intent to carry it out. Have you started to work out or worked out the details of how to kill yourself? Do you intend to carry out this plan? If yes, describe:							
INTENSITY OF IDEATION	•						
being the least severe and 5 being the most severe). Most Severe Ideation: Type # (1-5) Description of Ideation	Most Severe						
Frequency How many times have you had these thoughts?							
(1) Less than once a week (2) Once a week (3) 2-5 times in week (4) Daily or almost daily (5) Many times each day Duration							
When you have the thoughts, how long do they last? (1) Fleeting - few seconds or minutes (4) 4-8 hours/most of day (2) Less than 1 hour/some of the time (5) More than 8 hours/persistent or continuous (3) 1-4 hours/a lot of time							
Controllability Could/can you stop thinking about killing yourself or wanting to die if you want to? (1) Easily able to control thoughts (4) Can control thoughts with a lot of difficulty (2) Can control thoughts with little difficulty (5) Unable to control thoughts (3) Can control thoughts with some difficulty (0) Does not attempt to control thoughts							
Deterrents							
Are there things - anyone or anything (eg, family, religion, pain of death) - that stopped you from wanting to die							
or acting on thoughts of committing suicide? (1) Deterrents definitely stopped you from attempting suicide (4) Deterrents most likely did not stop you							
(2) Deterrents probably stopped you (5) Deterrents definitely did not stop you (3) Uncertain that deterrents stopped you (0) Does not apply							
Reasons for Ideation							
What sort of reasons did you have for thinking about wanting to die or killing yourself? Was it to end the pain							
or stop the way you were feeling (in other words you couldn't go on living with this pain or how you were							
feeling) or was it to get attention, revenge or a reaction from others? Or both? (1) Completely to get attention, revenge or a reaction from others (4) Mostly to end or stop the pain (you couldn't go on) (2) Mostly to get attention, revenge or a reaction from others living with the pain or how you were feeling (3) Equally to get attention, revenge or a reaction from others (5) Completely to end or stop the pain (you couldn't go on and to end/stop the pain living with the pain or how you were feeling) (0) Does not apply							

SUICIDAL BEHAVIOR	Since Last					
(Check all that apply, so long as these are separate events; must ask about all types)	Visit					
Actual Attempt:	Yes No					
A potentially self-injurious act committed with at least some wish to die, as a result of act. Behavior was in part thought of as	пп					
method to kill oneself. Intent does not have to be 100%. If there is any intent/desire to die associated with the act, then it can be						
considered an actual suicide attempt. There does not have to be any injury or harm, just the potential for injury or harm. If	Total # of Attempts					
person pulls trigger while gun is in mouth but gun is broken so no injury results, this is considered an attempt.	Attempts					
Inferring Intent: Even if an individual denies intent/wish to die, it may be inferred clinically from the behavior or circumstances.	Yes No					
For example, a highly lethal act that is clearly not an accident so no other intent but suicide can be inferred (eg, gunshot to head, in the property of a high floor/story). Also, if company decise intent to die but they they that they did could be						
jumping from window of a high floor/story). Also, if someone denies intent to die, but they thought that what they did could be lethal, intent may be inferred.						
Have you made a suicide attempt?						
Have you made a smedle altempt. Have you done anything to harm yourself?						
Have you done anything dangerous where you could have died?						
What did you do?						
Did you as a way to end your life?						
Did you want to die (ayan a little) when you 2						
Did you want to die (even a little) when you? Were you trying to end your life when you?						
Or did you think it was possible you could have died from ?						
Or did you do it purely for other reasons / without ANY intention of killing yourself (like to relieve stress, feel						
